## 2.2 Purpose of the Study

The purpose of the study is to evaluate the adaptation of product use in adult, current cigarette smoking subjects between baseline and after 1 month of use of one of two P3P variants.

The effect of P3P use behavior on nicotine pharmacokinetic (PK) profile, acceptability, as well as the safety and tolerability of P3P over a period of 1 month will be investigated. In addition, the overall use of tobacco and nicotine containing products will be monitored.

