#### **Confidentiality Statement**

Data and information contained in this document are considered to constitute trade secrets and confidential commercial information, and the legal protections provided to such trade secrets and confidential information are hereby claimed under the provisions of applicable law. No part of this document may be publicly disclosed without the written consent of Philip Morris Products S.A.

In a previous study conducted with P3P (ClinTrials.gov: NCT03369340), the pharmacokinetic profiles of nicotine following a single use of P3P were indicative of a partial pulmonary and partial oromucosal absorption with lower plasma nicotine levels compared to published data for single cigarette smoking (23, 24). It is well established that changing a current cigarette to a novel tobacco /nicotine-containing product requires an adaptation in product use behavior as has been described for low-yield cigarettes, e-cigarettes or a novel Tobacco Heating System (10-15). The changes in product use behaviour over time (e.g. potential changes in puffing/inhalation process) may result in changes in the nicotine PK profiles in particular in the absorption phase. For this reason, nicotine PK profiles and parameters following a single product use will be assessed at the beginning of the exposure period (Day 1) and at the end of the exposure period following adaptation to product use (Day 30). Sampling timepoints for determination of nicotine concentrations were selected to ensure reliable estimation of PK parameters.

Plasma nicotine presents a biphasic profile, with a typical rapid initial disposition half-life ( $t_{1/2\alpha}$ ) of 1.35 hours, followed by a slower terminal elimination half-life ( $t_{1/2\beta}$ ) of 17 hours (28). To ensure a full nicotine washout between each product use, a separation of 3 days would have been required ( $\sim 5 \times$  elimination  $t_{1/2\beta}$ ). Based on nicotine population PK modeling, it was estimated that subjects' nicotine has entered in the terminal elimination phase with concentrations decreasing according to the terminal elimination rate constant ( $\lambda_z$ ) after 8 to 10 hours post administration. As a consequence, a minimum of 10 hours have been established in this study design before the start of product use for PK assessment to ensure appropriate washout of nicotine. Background-concentration correction will be applied to adjust for any residual carry-over effects as detailed in section 12.5.1.

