5 STUDY OBJECTIVES AND ENDPOINTS

5.1 Primary Objective and Endpoints

1. To assess nicotine pharmacokinetics following use of a single P3P-1mg or P3P-2mg product on Day 1 and Day 30.

Endpoints:

- Plasma nicotine time-concentration profile from prior product use to 4 hours post start of product use;
- PK parameters: maximum plasma concentration (C_{max}); time to maximum concentration (t_{max}); Area under the concentration-time curve from start of product use to 4 hours ($AUC_{(0-4h)}$).

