12.5 Planned Statistical Analyses

12.5.1 Primary Analyses of PK parameters

An analysis of covariance (ANCOVA) will be conducted at Day 30 on background-corrected $AUC_{(0-4h)}$ ($cAUC_{(0-4h)}$) and background-corrected C_{max} (cC_{max}) endpoints in the natural logarithmic scale. The model will include sex and variant as factors and value at Day 1 in the natural logarithmic scale as a covariate. The results of this analysis for each of $cAUC_{(0-4h)}$ and cC_{max} will be presented as geometric least square means and 95% confidence intervals for each variant and least square mean ratio and 95% confidence intervals of P3P-2mg:P3P-1mg ratio.

The same ANCOVA analysis will be performed for the $AUC_{(0-4h)}$ and C_{max} derived using uncorrected concentrations.

LS means for each product will be back-transformed by exponentiation and will be tabulated together with the ratio (P3P-2mg:P3P-1mg) and 95% CI.

In addition, least square mean ratio and 95% confidence intervals of Day 30 versus Day 1 will be provided by variant using an ANOVA model for the difference Day 30 – Day 1 in the natural logarithmic scale endpoints; the ANOVA model will have variant and sex as factors. LS means for each product will be back-transformed by exponentiation.

The geometric CV will also be presented as $CV(\%) = 100\sqrt{(e^{MSE} - 1)}$, where MSE is the mean square error of the fitted model residual.

Descriptive statistics for t_{max} will be provided by P3P variant, the p-value resulting from the non-parametric between-group comparison (Wilcoxon Rank Sum Test) will be reported. The Hodges-Lehman estimate for the between-group difference in median will be reported together with its 95% CI.

Descriptive statistics will be presented by sex (male or female) and by product exposure category.

For t_{max} , descriptive statistics by sex and product exposure will also be provided.

To better understand the impact of the higher than expected T_0 values, a sensitivity analysis of the Background-Corrected and Uncorrected $AUC_{(0-4h)}$ and C_{max} will be performed where data for subjects with their T_0 value $>5\%$ of their C_{max} value will be excluded from the analysis.

The data will be presented in the below outputs:

TFL number	Title
TABLES	
15.2.9.1	Descriptive Statistics of Background-Corrected and Uncorrected Pharmacokinetic Parameters of Nicotine (AUC _(0-4h) and C _{max}) at Day 1 and Day 30 – PK Population

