15.2.9.2	Analysis of Background-Corrected and Uncorrected Pharmacokinetic Parameters of Nicotine (AUC _(0-4h) and C _{max}) at Day 30 and at Day 30 relative to Day 1 – PK Population
15.2.9.3	Descriptive Statistics of Background-Corrected and Uncorrected Pharmacokinetic Parameters of Nicotine (AUC _(0-4h) and C _{max}) at Day 1 and Day 30 by Sex – PK Population
15.2.9.4	Descriptive Statistics of Background-Corrected and Uncorrected Pharmacokinetic Parameters of Nicotine (AUC _(0-4h) and C _{max}) at Day 1 and Day 30 by Product Exposure Category – PK Population
15.2.10.1	Descriptive Statistics of Background-Corrected and Uncorrected t _{max} at Day 1 and Day 30 - PK Population
15.2.10.2	Analysis of Background-Corrected and Uncorrected t _{max} at Day 1 and Day 30 – PK Population
15.2.10.3	Descriptive Statistics of Background-Corrected and Uncorrected t _{max} at Day 1 and Day 30 – by Sex - PK Population
15.2.10.4	Descriptive Statistics of Background-Corrected and Uncorrected t _{max} at Day 1 and Day 30 – By Product Exposure Category – PK Population
15.2.11.1	Sensitivity Analysis of Background-Corrected and Uncorrected Pharmacokinetic Parameter of Nicotine (AUC _(0-4h) and C _{max}) at Day 1 and Day 30 – PK Population
FIGURES	
15.3.1.1	Pharmacokinetic Parameters of Nicotine By P3P variant – PK Population
LISTINGS	
15.1.9.1	Listing of Background-Corrected Pharmacokinetic Parameters of Nicotine – PK Population
15.1.10.1	Listing of Background- Uncorrected Pharmacokinetic Parameters of Nicotine – PK Population

Pharmacokinetic Profiles

Geometric mean (95% CI) profiles, spaghetti plots of individual PK profiles for each subject will also be presented by timepoint.

For the analysis and graphical presentation of plasma concentrations, the nominal timepoints will be used. Plasma concentration data will also be listed along with the details of the actual collection times.

TFL number	Title
TABLES	
15.2.12.1	Descriptive Statistics of Background-Corrected Plasma Nicotine Concentration at Day 1 and Day 30 by Timepoint– PK Population
15.2.12.2	Descriptive Statistics of Uncorrected Plasma Nicotine Concentration at Day 1 and Day 30 by Timepoint– PK Population
15.2.12.3	Descriptive Statistics of Background-Corrected Plasma Nicotine Concentration at Day 1 and Day 30 by Timepoint by Sex – PK Population
15.2.12.4	Descriptive Statistics of Background-Corrected Plasma Nicotine Concentration at Day 1 and Day 30 by Timepoint by Product Exposure Category – PK Population

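### No within-variant Day 30 versus Day 1 estimate, interval or test is specified for tmax, a primary endpoint, although the protocol looks for adaptation in the absorption phase

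*SAP*

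**What the plan says.** Protocol 2.2 gives the purpose as "to evaluate the adaptation of product use in adult, current cigarette smoking subjects between baseline and after 1 month of use". Protocol 4.2 explains why PK is measured on both Day 1 and Day 30: changes in how the product is used "may result in changes in the nicotine PK profiles in particular in the absorption phase". tmax is one of the three PK parameters under the primary objective (Protocol 3.1, SAP 5.1). Protocol 12.1.2 makes Day 1 the baseline for changes in those parameters.

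SAP 12.5.1 then treats the primary parameters differently.

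- **AUC(0-4h) and Cmax.** A Day 30 ANCOVA compares the variants. In addition, "least square mean ratio and 95% confidence intervals of Day 30 versus Day 1 will be provided by variant using an ANOVA model", fitted to the difference on the log scale. The title of Table 15.2.9.2 accordingly covers results "at Day 30 and at Day 30 relative to Day 1 – PK Population".
- **tmax.** Descriptive statistics are planned by variant, sex and exposure category. For inference, "the p-value resulting from the non-parametric between-group comparison (Wilcoxon Rank Sum Test) will be reported", and the Hodges-Lehmann "estimate for the between-group difference in median will be reported together with its 95% CI". The title of Table 15.2.10.2 names an analysis at each of the two days, but not Day 30 relative to Day 1.

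SAP 12.1.3 restricts summaries of sampling-time endpoints to the median, quartiles and range. SAP 9 announces within-group Day 30 versus Day 1 comparisons by ANOVA under a general PK heading, and in the same place rules out comparisons at Day 1.

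**The concern.** Learning to draw on and inhale a new product would be expected to act in both variants. Protocol 2.1.2 reports a tmax of 15–22.5 minutes for the product in smokers new to it, against 5–8 minutes for cigarettes. If users of both variants move towards the lower figures, the difference between variants need not change at all.

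tmax is the planned parameter closest to speed of absorption; Cmax describes the height of the peak. As specified, the report would give an interval for tmax on the between-variant contrast and none on the within-subject contrast that the trial was set up to examine.

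**Working it through.** **1. What the planned comparison can see.** Let x_i be the Day 30 tmax values in one variant and y_j those in the other. The Hodges-Lehmann between-group estimate is the median of all differences y_j − x_i. Add a common shift δ to both variants:

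(y_j + δ) − (x_i + δ) = y_j − x_i

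The estimate does not move. The joint ranks do not move either, and they are also unchanged if both variants are multiplied by the same factor, so the rank-sum p-value is the same. A paired estimate built on d_i = (Day 30 − Day 1) within subject does move, by δ.

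**2. Size.** The plan has no power figure to reproduce. SAP 8 calls the 60 subjects empirically based, Protocol 12.1.5 gives no significance level, and neither document gives an effect size or SD. The following simulation is therefore an illustration.

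- From the documents: about 30 subjects per variant (SAP 8); Day 1 median of 15 or 22.5 minutes (the range in Protocol 2.1.2); sampling at 4, 7, 10, 15 and 30 minutes and 1, 2 and 4 hours (SAP Table 11).
- Assumed: lognormal true tmax with log SD 0.5 or 0.8, assigned to the nearest sampling time on the log scale; within-subject correlation 0.3; no dropout; two-sided 5% level; the same Day 30/Day 1 ratio in both variants; zero differences dropped from the signed-rank test; 4,000 runs per row.

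The table gives the percentage of runs. The last column is the share in which one variant's Day 1 and Day 30 medians were identical.

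| Day 1 median (min) | Ratio | Log SD | Rank-sum, Day 1 | Rank-sum, Day 30 | Paired, one variant (30) | Paired, pooled (60) | Medians identical |
|---|---|---|---|---|---|---|---|
| 15 | 1.00 | 0.5 | 5.1 | 4.5 | 5.0 | 5.9 | 89.3 |
| 15 | 1.00 | 0.8 | 5.0 | 5.2 | 4.8 | 5.0 | 63.6 |
| 15 | 0.75 | 0.5 | 4.2 | 5.1 | 60.6 | 89.4 | 19.7 |
| 15 | 0.75 | 0.8 | 4.5 | 4.9 | 28.6 | 51.8 | 27.6 |
| 15 | 0.50 | 0.5 | 5.0 | 5.0 | 100.0 | 100.0 | 0.1 |
| 15 | 0.50 | 0.8 | 5.2 | 4.9 | 92.2 | 99.8 | 1.3 |
| 22.5 | 1.00 | 0.5 | 4.8 | 5.0 | 5.0 | 4.9 | 53.5 |
| 22.5 | 1.00 | 0.8 | 5.2 | 4.6 | 4.9 | 5.0 | 49.2 |
| 22.5 | 0.75 | 0.5 | 5.0 | 5.1 | 60.6 | 88.7 | 25.0 |
| 22.5 | 0.75 | 0.8 | 5.0 | 5.6 | 30.2 | 52.7 | 30.2 |
| 22.5 | 0.50 | 0.5 | 4.5 | 4.9 | 100.0 | 100.0 | 2.5 |
| 22.5 | 0.50 | 0.8 | 5.6 | 5.0 | 92.2 | 99.8 | 4.8 |

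The rank-sum test stays at its nominal level throughout, as step 1 requires.

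**3. What side-by-side medians can see.** With no shift, the two medians still differ in 100 − 89.3 = 10.7% to 100 − 49.2 = 50.8% of runs. With a 25% shortening they differ in 100 − 30.2 = 69.8% to 100 − 19.7 = 80.3%. With a 50% shortening they differ in 95.2–99.9%. A change in the median is thus telling for a large shift, but weak evidence for a modest one.

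**4. A second set of assumptions.** Take 25 subjects per variant and correlation 0.4. Let the shares with tmax at 4/7/10/15/30 minutes go from 3/7/10/40/40% on Day 1 to 10/25/25/30/10% on Day 30 in both variants. The rank-sum test rejects in about 4% of runs, the paired test within one variant in 96–97%. That is a large shift: with three quarters, half and a quarter of it, the paired test rejects in about 77%, 41% and 15%.

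**The case against.** The study is declared descriptive (SAP 5.3.1), and SAP 12.1.6 says that no claim will rest on individual intervals. tmax is tabulated at both days. Concentrations are summarized at every timepoint for both days, and geometric mean profiles with 95% CIs and individual profiles are plotted. Cmax and AUC(0-4h) have Day 30/Day 1 ratios with intervals, and puffing and inhalation behavior has shift tables. SAP 12.1.3 adds change from baseline where applicable, and SAP 9 speaks of within-group PK comparisons generally.

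Much of this stands. A reader might infer from the missing comparison that a shift common to both variants could not be detected, or that the trial would report no effect. The documents do not support that. Under the large shift in step 4 of the working, the population quartiles go from 15/15/30 to 7/10/15 minutes. In simulation the Day 30 sample median was below the Day 1 median in 88% of runs, and in 99.9% at least one quartile fell and none rose. The rank-sum test does not fail either; it answers another question.

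A reader might also infer that the samples at 4 to 15 minutes go unused. They feed the timepoint summaries and profiles. A log-scale partial AUC to 15 minutes would not be a safe addition. Background-corrected early values can be zero or negative, Cmax of the 1 mg variant was only 1.1 ng/mL in the earlier study (Protocol 2.1.2), and the SAP has no rule for such values.

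None of this supplies a paired estimate or interval for tmax. The where-applicable clause and SAP 9 do not name it, and SAP 9 relies on ANOVA, which SAP 12.5.1 applies to log-scale endpoints only. The separate table shells might add a change from Day 1, but the SAP text does not ask for one. The descriptive label does not explain why tmax receives an interval between variants but none for adaptation.

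**Conclusion.** The point holds as a gap in specification: SAP 12.5.1 provides no within-variant Day 30 versus Day 1 estimate, CI or test for tmax. The comparison it does provide is uninformative about a common shift by construction, whatever the distribution of tmax.

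The gain from a paired analysis depends on assumptions. Per variant, it rejects in 29–61% of runs for a 25% shortening and 92–100% for a 50% shortening, with 30 complete pairs, log SD 0.5–0.8 and correlation 0.3. Fewer complete pairs would lower these figures. For large shifts the planned descriptive output would already show the change, so what is added is mainly an estimate with its uncertainty for modest shifts. This is an inexpensive improvement that lets the trial answer its own within-subject question; it does not invalidate the plan.

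**What to change.** - In SAP 12.5.1 and Table 15.2.10.2, add for each variant the paired Day 30 minus Day 1 difference in tmax, background-corrected and uncorrected, as a Hodges-Lehmann estimate with 95% CI from the signed-rank procedure. Limit it to subjects with tmax on both days.
- State how ties and zero differences from the sampling grid are handled. Also state whether actual or nominal times are used, because SAP 7.1 derives PK parameters from actual sampling times and differences of a minute or two may reflect only the sampling windows.
- Add change from Day 1 to Table 15.2.10.1.
- Reconcile SAP 9, which rules out Day 1 comparisons, with the title of Table 15.2.10.2, which includes an analysis at Day 1.

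The cost is SAP wording and a few more reported rows; no new data are needed. One caution on reading: use is ad libitum for up to 15 minutes (Protocol 6.2.2), so tmax also reflects how long the product was used. The paired result should be read alongside the recorded start and stop times.

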#### 12.1.1 Stratification Criteria

The sample randomization will enforce at least 40% of each sex in each product variant. Analyses stratified by sex will be detailed in the SAP.

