6.3 Product Allocation and Blinding

6.3.1 Methods of Assigning Subjects to Product Variant

At Day -1, after product test, subjects who confirmed their willingness to continue in the study will be randomized using an interactive web response system (IWRS). Subjects will be randomized to one of the two arms: P3P-1mg or P3P-2mg in a 1:1 ratio.

Each randomization group (P3P-1mg, P3P-2mg) will be stratified on sex distribution to ensure that at least 40% of each sex is randomized in each group.

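### The tmax comparison between variants ignores the sex stratum that randomization and every other between-variant model use; the planned test is valid but can be conservative, and stratifying it costs almost nothing

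*SAP*

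**What the plan says.** SAP 5.1 lists tmax among the primary PK parameters, with Cmax and AUC(0-4h). For tmax, SAP 12.5.1 states that "the p-value resulting from the non-parametric between-group comparison (Wilcoxon Rank Sum Test) will be reported" and adds: "The Hodges-Lehman estimate for the between-group difference in median will be reported together with its 95% CI". Neither sentence mentions sex. The output is Table 15.2.10.2, which covers corrected and uncorrected tmax. Sex enters the tmax outputs only through the descriptive Table 15.2.10.3.

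On allocation, SAP 6.3.1 says "Subjects will be randomized to one of the two arms: P3P-1mg or P3P-2mg in a 1:1 ratio" and that each randomization group "will be stratified on sex distribution to ensure that at least 40% of each sex is randomized in each group". Protocol 12.1.1 puts it this way: "The sample randomization will enforce at least 40% of each sex in each product variant".

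The other between-variant analyses all carry sex. For cAUC, cCmax and their uncorrected versions, SAP 12.5.1 says: "The model will include sex and variant as factors and value at Day 1 in the natural logarithmic scale as a covariate". The ANCOVAs for VAS-craving AUC (SAP 12.5.2.1) and for the Product Experience subscales (SAP 12.5.2.3) also have sex as a factor.

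**The concern.** When allocation is stratified, the analysis should normally use the stratum. If the arms have the same sex mix, a sex difference in tmax adds the same amount to both arms, so it adds nothing to the real sampling variation of the between-arm contrast. The plain rank-sum test still counts the between-sex spread in its null variance. Its p-value is then too large and, by the same mechanism, its interval would tend to be too wide.

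If the arms differ in sex mix, part of any sex difference in tmax appears as a variant difference.

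The tmax test is the only planned between-variant test without protection against either effect, and the SAP gives no reason for treating it differently. tmax describes the timing of absorption, and Protocol 4.2 expects changes in use behaviour to show mainly in the absorption phase.

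**Working it through.** **Inputs from the documents.** 60 subjects, about 30 per arm, 1:1 (SAP 8, 6.3.1). Post-T0 samples at 4, 7, 10, 15, 30, 60, 120 and 240 minutes (SAP 11.2.1). At least 40% of each sex per arm: 0.40 × 30 = 12, so each sex numbers 12 to 18 in an arm. The sample size is empirical, so there is no power figure to reproduce.

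**Assumed inputs.** Log-normal tmax with median 18 minutes and log SD 0.7; a true variant shift of 0.75 SD, a ratio of exp(0.75 × 0.7) = 1.69; a two-sided 5% rule; sex effects from 0 to 1.5 SD. The documents supply none of these.

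**Tests compared.** Plain Wilcoxon: z = (W − n₁(N+1)/2)/√V, with V = [n₁n₀/(N−1)] × mean squared deviation of the ranks, which corrects for ties. Van Elteren: the same quantities within each sex, combined as Σw(W−E)/√(Σw²V), with w = 1/(n_s+1) for a stratum of n_s subjects.

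**Hand check with normal theory, 15 men and 15 women per arm.** A sex effect of δ SD adds δ²/4 to the variance that the plain test uses, but nothing to the true variance of the contrast. The effective critical value becomes 1.96 × √(1 + δ²/4), and the expected z is 0.75 × √(30/2) = 2.905.
- Stratified, or no sex effect: size 5.0%, power Φ(2.905 − 1.960) = 0.828.
- δ = 0.5: critical value 2.020, size 4.3%, power Φ(0.885) = 0.812, a loss of 1.6 points.
- δ = 1.0: critical value 2.191, size 2.8%, power Φ(0.714) = 0.762, a loss of 6.6 points.

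**Simulation, same balance, tmax rounded to the sampling times, 8,000 runs per scenario** (simulation error about ±0.005 on size and ±0.01 on power):

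| Sex effect (SD) | Ratio of tmax between sexes | Size, plain | Size, stratified | Power, plain | Power, stratified |
|---|---|---|---|---|---|
| 0 | 1.00 | 0.044 | 0.045 | 0.772 | 0.767 |
| 0.25 | 1.19 | 0.047 | 0.048 | 0.773 | 0.772 |
| 0.5 | 1.42 | 0.043 | 0.049 | 0.764 | 0.779 |
| 1.0 | 2.01 | 0.030 | 0.050 | 0.686 | 0.763 |
| 1.5 | 2.86 | 0.015 | 0.051 | 0.592 | 0.771 |

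At 1.0 SD the loss is 0.763 − 0.686 = 0.077. At 0.5 SD it is 0.779 − 0.764 = 0.015, near simulation error. A run without rounding to nominal times gave the same picture (about 70% against 77% power at 1.0 SD). That matters because SAP 7.1 uses actual sampling times.

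**If allocation is only a 40% quota.** The extreme allowed split is 18 men and 12 women in one arm against 12 and 18 in the other. The sex mix then differs by 18/30 − 12/30 = 0.20, so a sex effect of δ shifts the variant contrast by 0.20δ SD: 0.10 SD at δ = 0.5 and 0.20 SD at δ = 1.0. The latter is a spurious tmax ratio of exp(0.20 × 0.7) = 1.15. Simulated size of the plain test was 0.063, 0.080 and 0.100 at 0.5, 1.0 and 1.5 SD; the stratified test stayed between 0.049 and 0.053. Power of the plain test at 0.5 SD was 84% or 63%, depending on direction, against about 75% stratified (4,000 runs). All these figures require the quota reading and the most unequal split it allows.

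**Not checked.** Only the tests were simulated. The Hodges-Lehmann interval, planned or stratified, was not, so the statement about its width rests on the mechanism alone.

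**The case against.** The strongest reply is that the planned test is sound. Both documents describe the randomization as stratified on sex. If that means balanced lists within sex, the plain Wilcoxon test controls its error rate and is at worst conservative. This stands.

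The inputs are also generous. Sex effects of 0.5 and 1.0 SD mean 1.4-fold and 2-fold differences in tmax between men and women. The only P3P tmax data in the documents (Protocol 2.1.2) run from 15 to 22.5 minutes across four variants, a 1.5-fold range, and no sex difference is reported. The assumed 1.69-fold variant shift also exceeds that range. This stands too, and is why the size of the loss can only be given conditionally.

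Third, size and power presuppose a 5% decision rule. SAP 5.3.1 calls the study descriptive, Protocol 12.1.5 marks the significance level as not applicable, and SAP 12.1.6 rests no claim on individual intervals. Both documents' sections on descriptive statistics plan only medians, quartiles and range for tmax; the test is an addition in SAP 12.5.1. This lowers the stakes but does not remove the point: once a p-value and a 95% CI are reported for a primary endpoint, they should reflect the design as those of the other endpoints do. Table 15.2.10.3 would let a reader see a sex difference, but gives no adjusted comparison.

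A reader might go further and infer that the tmax result is biased, or that its error rate exceeds 5%. The documents do not support that. It needs arms that differ in sex mix and a sex effect on tmax; stratified 1:1 allocation works against the first, and nothing in the documents shows the second.

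**Conclusion.** The inconsistency is real and its consequence small. With sex balanced across arms, the planned tmax and ctmax test is valid and, if tmax differs by sex, conservative. Under the assumed inputs the loss is negligible up to a 0.5 SD sex effect and about 7 to 8 power points at 1.0 SD, where actual size is about 3%. With no sex effect nothing is lost.

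A shift in the comparison itself is possible in two situations only: the 40% wording describes a quota without balance within sex, or the exclusions that define the PK population (SAP 10.4) leave the arms with different sex mixes. The documents do not settle the first, and the second cannot be known in advance. This is a cheap improvement in efficiency and consistency, not a threat to the study's conclusions.

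**What to change.** In SAP 12.5.1 and Table 15.2.10.2, compare tmax and ctmax between variants with the van Elteren test stratified by sex. Report a sex-stratified (aligned) Hodges-Lehmann estimate with its 95% CI and call it a location shift, since it is not in general a difference in medians. Keep the unstratified test and estimate as supportive. If the unstratified version is to remain the main one, say why.

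It would also help to state in SAP 6.3.1 whether the lists are balanced within sex or only subject to the 40% minimum.

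The cost is a sentence or two in the SAP and the programming of one table. Sex is already recorded, so no new data are needed. The statistical downside is 0 to 2 points of power if sex has no effect on tmax.

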One pharmacokinetic clinical study was conducted with P3P in 19 smokers in Switzerland (ClinTrials.gov: NCT03369340). In this study, following a single use of four P3P variants, nicotine  $C_{max}$  was 1.1 ng/mL for the 1 mg variant and between 2.1 and 3.1 ng/mL for the 2 mg variants and was reached after 15-22.5 minutes ( $T_{max}$ ).  $C_{max}$  values for P3P were lower compared to literature-reported  $C_{max}$  for cigarettes which ranges between 10-30 ng/mL (23-25) or Nicorette® Inhalator, a nicotine replacement therapy, for which  $C_{max}$  values of 6-8 ng/mL have been described (25, 26).  $T_{max}$  was at a later timepoint for P3P compared to cigarettes for which maximal plasma concentration is reached after 5-8 minutes, but earlier compared to Nicorette® Inhalator for which  $T_{max}$  is at 30 minutes. Thus, the observed concentration-time profile for P3P is indicative of a partial pulmonary and partial oromucosal absorption compared to the pulmonary absorption for cigarettes and the oromucosal absorption of Nicorette® inhalator. The adaptation of the product use behavior in these subjects, which were unfamiliar with P3P may have been incomplete. The product was generally well tolerated and no safety concern was revealed.

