7.1 Pharmacokinetic Parameters

For the calculation of PK parameters, the actual blood sampling times (collected in the CRF) rather than the nominal timepoints will be used in all calculations with the exception of the last collected sample prior to product use which can be considered as the T_0 value. Partial dates/times for PK assessments or T_0 will not in general be imputed.

For nicotine concentrations below the lower limit of quantification (BLOQ) :

- BLOQ values before T_0 will be imputed by LLOQ/2.
- BLOQ values after the last quantifiable value are not included in the analysis (e.g., for the calculation of AUC).
- Any BLOQ value (after T_0 and before the last quantifiable value) would need to be queried and, if confirmed, it will be imputed by LLOQ/2.

To minimize the carry-over effect in the plasma nicotine PK parameters due to limited washout periods, background-concentration correction will be applied to the nicotine concentration data.

Baseline nicotine concentration (C_0) will be defined as the last measured concentration prior to T_0 at Day 1 and at Day 30 (Visit 2 and Visit 6). The baseline correction will be implemented by calculating the PK parameters using adjusted concentration values as described below:

- Calculate the slope using a linear regression on the log concentration of the 3 pre- T_0 timepoints.
- If the slope is ≤ 0 , then use the slope to determine the elimination rate constant λ_z .

- If the slope is > 0 , then use the subject's slope that is ≤ 0 from the other visit to determine λ_z . If the subject's slopes are positive for the 2 visits, baseline corrected PK parameters will not be calculated.
- Adjust each concentration value post-baseline using the following formula:

$$cC_t = C_t - C_0 * e^{-\lambda_z t}.$$

cC_t is the corrected concentration at each time point, C_t is the concentration at each time point, C_0 is the pre-use baseline nicotine concentration at the given visit, λ_z is the elimination rate constant and t is the actual time.

If C_0 is BLOQ then there will be no baseline correction of the PK parameters. In that case cC_{max} , ct_{max} and $cAUC_{(0-4h)}$ will be considered as equal to C_{max} , t_{max} and $AUC_{(0-4h)}$, respectively.

- The following PK parameters will be derived from nicotine levels adjusted for baseline:

cC_{max}	Background-corrected maximum observed plasma concentration. cC_{max} will be reported as long as there is at least one quantifiable concentration post-exposure

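### The sensitivity analysis for high T0 values excludes subjects by reference to their own Cmax, so its result is confounded by selection on the endpoint it reports.

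*SAP*

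**What the plan says.** SAP 12.5.1 gives the purpose: "To better understand the impact of the higher than expected" T0 values. The analysis covers corrected and uncorrected AUC(0-4h) and Cmax. It "will be performed where data for subjects with their" T0 value above 5% "of their C_{max} value will be excluded from the analysis". The output is Table 15.2.11.1, for Day 1 and Day 30. The main effect measure in the same section is the "least square mean ratio and 95% confidence intervals of P3P-2mg:P3P-1mg ratio".

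Three other passages bear on the rule:

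- Protocol 4.2 recognises that nicotine will not be fully washed out. It gives a terminal half-life of 17 hours, says full washout would need about 3 days, and states that "a minimum of 10 hours have been established in this study design before the start of product use for PK assessment".
- Protocol 2.1.2 reports that in an earlier single-use study of 19 smokers Cmax "was 1.1 ng/mL for the 1 mg variant and between 2.1 and 3.1 ng/mL for the 2 mg variants".
- SAP 7.1 states that "BLOQ values before T_0 will be imputed by LLOQ/2". The LLOQ is not given.

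The SAP gives no C0 values and no expected number excluded. It does not say whether the rule uses corrected or uncorrected Cmax, or whether failing at one visit removes that visit or the whole subject.

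**The concern.** A sensitivity analysis for background nicotine should change the amount of background and leave the rest of the comparison alone. This rule also changes who is compared, according to how much nicotine they absorbed. Two subjects with the same C0 are treated differently if one reaches a higher Cmax, and the one kept is the one with the larger outcome.

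At stake is how Table 15.2.11.1 can be read. A shift from the main analysis could come from background or from selection, and the table cannot separate them. For the same reason, agreement with the main analysis would not by itself show robustness. Because the two variants deliver different amounts of nicotine, the selection can also act unequally on the arms and reach the 2mg:1mg ratio.

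**Working it through.** The plan attaches no calculation to the 5% rule, so there is no figure to reproduce.

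**Inputs from the documents.** Cmax 1.1 ng/mL (1 mg) and 2.1 to 3.1 ng/mL (2 mg), Protocol 2.1.2; about 30 per arm, SAP 8; allocation, SAP 6.3.1: "Subjects will be randomized to one of the two arms: P3P-1mg or P3P-2mg in a 1:1 ratio".

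**Assumptions, not in the documents.** Product-derived Cmax (R) is log-normal with CV 40% to 70%. Median C0 is 0.03 to 0.2 ng/mL with CV 80%, the same in both arms and independent of R. The earlier study's Cmax values serve as geometric means of R.

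**Step 1: the limit in ng/mL.** Limit = 0.05 × Cmax.

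- 1 mg: 0.05 × 1.1 = 0.055.
- 2 mg: 0.05 × 2.1 = 0.105, to 0.05 × 3.1 = 0.155.
- Ratio of limits: 2.1/1.1 = 1.91 to 3.1/1.1 = 2.82.

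If an imputed LLOQ/2 counts as the T0 value, a typical 1 mg subject with an unquantifiable C0 would still be excluded when LLOQ exceeds 2 × 0.055 = 0.11 ng/mL. For 2 mg the figure is 0.21 to 0.31 ng/mL.

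**Step 2: the rule in terms of the endpoint.** Take Cmax as C0 + R. Retention requires C0 ≤ 0.05 × (C0 + R), that is R ≥ (0.95/0.05) × C0 = 19 × C0. The rule is therefore a lower bound on R, the quantity being estimated.

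**Step 3: share retained if every subject had the same C0.** P = Φ[(ln g − ln(19 × C0))/σ], where g is the geometric mean of R and σ = √ln(1 + CV²). At CV 50%, σ = 0.472:

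| C0, ng/mL | 1 mg | 2 mg |
|---|---|---|
| 0.03 | 92% | about 100% |
| 0.05 | 62% | 95–99% |
| 0.1 | 12% | 58–85% |
| 0.2 | 0.4% | 11–33% |

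Letting C0 vary between subjects (CV 80%) softens this: at median C0 0.1 it becomes 26% against 55–72%.

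**Step 4: effect on the estimates.** I simulated 2,000,000 subjects per arm with background correction made perfect, so that background has no true effect on corrected Cmax. The step 2 rule was then applied (simulation error about 0.01 in the ratios).

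| CV of R | Median C0 | Retained of 30, 1 mg vs 2 mg | 1 mg geometric mean (true 1.10) | Ratio, true 1.91 | Ratio, true 2.82 |
|---|---|---|---|---|---|
| 40% | 0.03 | 23.8 vs 28.4–29.5 | 1.18 | 1.82 | 2.66 |
| 40% | 0.05 | 17.2 vs 25.2–27.9 | 1.25 | 1.78 | 2.55 |
| 40% | 0.1 | 7.4 vs 16.5–21.9 | 1.39 | 1.72 | 2.42 |
| 40% | 0.2 | 1.8 vs 6.9–12.0 | 1.59 | 1.69 | 2.33 |
| 70% | 0.03 | 22.7 vs 27.5–28.9 | 1.31 | 1.72 | 2.45 |
| 70% | 0.05 | 16.8 vs 23.9–26.9 | 1.48 | 1.65 | 2.28 |
| 70% | 0.1 | 8.4 vs 16.3–21.0 | 1.82 | 1.57 | 2.10 |
| 70% | 0.2 | 2.8 vs 8.0–12.4 | 2.33 | 1.52 | 1.97 |

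Every shift in the table comes from selection alone.

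**Step 5: when C0 differs by arm.** Suppose C0 scales with variant strength (×1.91 or ×2.82 on 2 mg). Then R/C0 has the same distribution in both arms, equal shares are retained, and the ratio stays at 1.91 or 2.82. The geometric means are still inflated: at CV 50% the 1 mg value rises from 1.10 to 1.22 at median C0 0.03, and to 1.82 at 0.2.

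**The case against.** The cut-off is 5% in both arms. The endpoints are analysed as logs and reported as ratios, and on that scale background distorts uncorrected Cmax through its share of Cmax. At C0 0.1 ng/mL the share is 0.1/1.2 = 8% for a typical 1 mg subject, against 0.1/3.2 = 3% to 0.1/2.2 = 5% for 2 mg. A relative limit holds contamination equal; a common absolute limit does not. This stands. A reader might infer from step 1 that the rule is biased against the 1 mg arm by construction, but the documents do not support that. The rule is stricter only in ng/mL, and step 5 shows the arms can be affected equally.

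A reader might also infer that the analysis is useless or would leave almost nobody. That needs C0 of roughly 0.2 ng/mL or more, and the SAP's remark that T0 values are higher than expected is not a number. Near 0.03 ng/mL most subjects stay. The earlier Cmax values are from first use in 19 smokers. They may not describe Day 30 after adaptation, and Protocol 2.1.2 does not say whether they are background-corrected.

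Finally, this is one supplementary table in a study described as descriptive (SAP 5.3.1), with no claim to rest on individual intervals (SAP 12.1.6). Background is also examined by running the full ANCOVA on corrected and uncorrected values. That limits the consequence and leaves the main estimates untouched. It does not repair the rule: no other section removes the dependence of retention on Cmax.

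**Conclusion.** The point holds as confounding by selection on Cmax. Inflation of the geometric means follows from the form of the rule whenever it excludes anyone, as long as C0 does not rise in step with absorption. The loss of more 1 mg subjects and the pull of the ratio toward 1 hold only if C0 is similar in the two arms; they shrink or vanish if Day 30 C0 scales with variant strength.

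The size depends on C0 and on the CV of Cmax, neither of which the documents give. It is smallest near a median C0 of 0.03 ng/mL (1.91 to 1.82 at CV 40%, 1.72 at CV 70%). At 0.1 ng/mL the retained 1 mg group is about 7 to 8 of 30, and the ratio falls to 1.72 or 1.57. The evidence does not support saying that the analysis cannot inform at all, or that the primary analysis is affected. It does support saying that a change seen in Table 15.2.11.1 cannot be attributed to high T0 values.

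**What to change.** Remove Cmax from the exclusion rule.

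- **Day 1.** Restrict on one absolute C0 cut-off, the same in both arms. Day 1 C0 reflects only use before randomization, including the product test of both variants, so it cannot depend on the assigned arm. Fix the cut-off before the randomization code is released for analysis. Because SAP 6.3.2 leaves sponsor and CRO personnel unblinded, record that it was set without sight of results by arm. SAP 9 drops Day 1 comparisons between variants, so these rows stay descriptive.
- **Day 30.** Keep all subjects. Show the ANCOVA with and without same-day log(C0), beside the corrected and uncorrected results. Label the adjusted version as conditioning on a post-randomization variable that may differ by variant.
- **Reporting.** Give numbers retained by variant and visit. State how values below LLOQ enter the rule.
- **If the 5% rule is kept.** Present it only as a descriptive supplement, and state which Cmax it uses and whether it removes a visit or a subject.

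The cost is SAP wording and one extra covariate, with no new data. The downside is that the Day 30 adjustment needs cautious reading. For example, suppose C0 doubles on 2 mg and log(C0) correlates 0.3 with log R (CV of R 50%, CV of C0 80%, log SDs 0.472 and 0.703). The slope is 0.3 × 0.472/0.703 = 0.20, and a true 1.91 reads 1.91/2^0.20 = 1.66.
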